## Protocol Summary

STUDY DRUG	Mirabegron 25-50mg daily
TITLE	Pilot study of mirabegron and behavioral modification including pelvic floor exercise for overactive bladder in multiple sclerosis ( MIRROR )
STUDY OVERVIEW	
A multi-center, randomized 1:1 placebo controlled 10-week study of mirabegron as add-on therapy to an educational intervention on behavioral modification including pelvic floor exercise (BM-PFE) to a cohort of 40 MS subjects with overactive bladder (OAB).
 
Active drug will be mirabegron 25mg daily with optional up-titration to 50mg daily after approximately 5 weeks. Subjects will be randomized at the Baseline Visit based on recordings in a voiding diary kept for 72 continuous hours in the screening period.
 
Voiding diaries of a 72 hour period each will be utilized during the screening period, between Phone Visit 1 and Titration and between Phone Visit 2 and Final Visit. In the diaries, subjects will record the time of each micturition and/or urgency episode, urine volume with each void (when available), any episode of incontinence, and the severity of urgency (Overactive Bladder Symptom Composite Score, OAB-SCS): 1 = no urgency (normal voiding); 2 = mild (could postpone voiding for as long as necessary without fear of incontinence); 3 = moderate (could postpone voiding for a short while without fear of leakage); 4= severe (could not postpone, had to rush to the toilet); 5= urgency incontinence (could not make it to the toilet without some leakage) Each voiding event is multiplied by the score for the event and then all events are summed to generate a total daily OAB-SCS cumulative score).
 
Primary outcome will be average daily OAB-SCS total score, Final Visit vs. Baseline. This accounts for the frequency, urgency and incontinence components of OAB.

RATIONALE	This design will demonstrate the effects of behavioral modification, including pelvic floor exercise on OAB through the placebo arm of the study. Adding mirabegron may yield greater results than BM-PFE alone. The standard starting dose is 25mg daily. An optional up-titration to 50mg is included, since some patients may respond better to the higher dosage. This titration will occur at about 5 weeks to allow a balanced period of time for recording response to the two dosages.
STUDY HYPOTHESIS	Treatment with Mirabegron will improve urinary urgency control beyond that achieved with pelvic floor exercises alone.
STUDY SUBJECTS	40 subjects with multiple sclerosis and OAB complaints.
DESIGN	Multiple-dose, randomized, placebo-controlled prospective, single-site, investigator-initiated trial.
DURATION OF STUDY	Approximately 10 weeks (active treatment)

TREATMENT REGIMEN	
Group A will receive Mirabegron 25mg daily      Group B will receive placebo      Group A and B will receive the same baseline education in pelvic floor exercise based on viewing of an instructional presentation plus take-home printed material.

TRIAL PERIODS	
Screening Period
 
 
• Screening to Baseline
 
 
Treatment Period
 
 
• Baseline to Final Visit (or Study Drug Discontinuation), includes Baseline, Phone Visit 1, Titration Visit, Phone Visit 2 and Final Visit
 

INCLUSION AND EXCLUSION CRITERIA	
Inclusion Criteria
 
 
• Confirmed diagnosis of MS (no sub-type restrictions)
 
• Age <math>\geq 18</math>
 
• No change in disease modifying therapy in 60 days.
 
• Patient willing and able to complete micturition diary
 
• Urinary urgency (8 or more entries of bladder urgency score <math>\geq 2</math>) in 72hr voiding diary recorded during screening period
 
• Micturition frequency <math>\geq 8</math> / day or incontinence <math>\geq 2</math> episodes in 72 hour voiding diary recorded during screening period
 
• At least 36 hours of voiding activity recorded in 72 hour voiding diary during screening period
 
• Non-antimuscarinic medications that are likely to influence bladder function may not be initiated between screening and study completion. They may be continued with no dose changes during the study.
 
• Discontinued use of antimuscarinics at least two weeks prior to screening
 
• Able to give informed consent
 
 
Exclusion Criteria
 
 
• Females who are breast-feeding, pregnant or have potential to become pregnant during the course of the study (fertile and unwilling/unable to use effective contraceptive measures)
 
• MS exacerbation within 30 days of screening
 
• Cognitive deficits that would interfere with the subject's ability to give informed consent or perform study testing
 
• Screening blood pressure <math>> 165</math> systolic or 100 diastolic
 
• History of allergy to Mirabegron
 
• Screening post-void residual <math>> 200</math>ml
 
• Evidence of urinary tract infection at screening
 
• Evidence of chronic inflammation such as interstitial cystitis, bladder stones, previous pelvic radiation therapy, or previous or current malignant disease of the pelvic organs
 
• Intravesical botulinum toxin treatment within the previous six months of screening.
 
• Presence of InterStim device
 
• Use of indwelling catheter or self-catheterization
 

	
 
Concurrent use of thioridazine (Mellaril® or Mellaril-S®), flecainide (Tambocor®), propafenone (Rythmol®) or digoxin (Lanoxin®)
 
Concurrent use of antimuscarinics: oxybutynin (Ditropan®, Ditropan XL®), tolterodine (Detrol®, Detrol LA®), fesoterodine extended-release (Toviaz®), solifenacina (Vesicare®), trospium (Sanctura®, Sanctura XR®), darifenacina extended release (Enablex®)
 
Screening estimated glomerular filtration rate (eGFR) < 60, AST or ALT > 2x upper limit of normal
 
Any other serious and/or unstable medical condition
 

NO. OF SUBJECTS	N= 40. This will include 20 subjects taking mirabegron and 20 subjects taking placebo.
EFFICACY (Outcome measures)	
Primary Outcome Measure:
 
 
Primary outcome will be Average daily OAB-SCS total score, Baseline vs. Final Visit
 
 
Secondary Outcome Measures based on voiding diary, compared to Baseline:
 
 
Titration Visit: Average daily OAB-SCS total score
 
Titration and Final Visit: A) mean # of micturitions/day; B) Mean number of incontinence episodes/day; C) Mean volume voided/micturition
 
 
Secondary Outcome Measures based on the following assessments at Titration Visit and Final Visit compared to Baseline:
 
 
Qualiveen Questionnaire
 
Subject Global Impression (single question)
 
PFE adherence question
 
Bladder Management Difficulties Questionnaire – Short Form (SCI-QOL v1.0)
 
 
Exploratory Outcome Measures based on the following assessments at Titration Visit and Final Visit compared to Baseline:
 
 
Bowel Management Difficulties Questionnaire – Short Form (SCI-QOL v1.0)
 

STATISTICAL METHODS	See Statistics section

SAFETY	All subjects will undergo baseline blood testing, CBC and CMP. Subjects with screening estimated glomerular filtration rate (eGFR) < 60, or AST or ALT > 2x upper limit of normal will be excluded. At screening, subjects reporting dysuria, fever or abdominal pain will undergo urine analysis, culture and sensitivity at the discretion of the principal investigator. Subjects with blood pressure > 165 systolic or > 100 diastolic will be excluded at screening or will discontinue study drug if this occurs during treatment period. However, they may complete other elements of the study. Subjects with screening post-void residual > 200ml will be excluded. Symptoms of urinary retention will be monitored throughout the study and may lead to early discontinuation of study drug; however, such subjects may complete other elements of the study. Subjects with a range of health conditions that may put the patient at risk for adverse outcomes will be excluded, as listed under Exclusion Criteria. Female subjects will undergo urine pregnancy testing if they are deemed to have any risk of being pregnant or becoming pregnant during the study.
ESTIMATED BUDGET	A budget estimate will be provided separately
SCHEDULE OF EVENTS	Refer to the Schedule of Study Assessments, Appendix 2 for timing of procedures
STUDY TIMELINE	Start-up 2 months, period of enrollment 22 months, data analysis and final report 3 months

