## Objective

To assess the effect of pelvic floor exercise education with or without mirabegron (MBG) on overactive bladder symptoms in people with multiple sclerosis (MS) based on the OAB Symptom Composite Score.

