Pelvic floor rehabilitation has a well-established role in the management of stress incontinence and idiopathic OAB. There is some evidence that pelvic floor exercise taught by physiotherapists over multiple sessions improves OAB in MS. However, access to pelvic floor physical therapy is limited by third-party payer coverage, availability of therapists with the necessary expertise and incurred expenses and time requirements for the patients. Behavioral modification, including pelvic floor exercise (BM-PFE) may be provided in a clinical setting using relevant educational materials. The BM-PFE component will offer an important educational benefit to all subjects interested in this study. Our center has a strong pelvic rehabilitation program with three therapists who are well-suited to produce the educational component of this study.

Adding MGB may yield greater results than BM-PFE alone. The standard starting dose is 25mg daily. An optional up-titration to 50mg is proposed, since some patients may respond better to the higher dosage, based on a Phase III trial including 25mg and 50mg daily treatment arms. This titration will occur at visit 3; 32-40 days post Baseline Visit, to allow a balanced period of time for recording response to the two dosages. Both dosages have been reported to be effective in treating OAB within 12 weeks.

This study explores the benefits of combining a brief BM-PFE educational program with a pharmacotherapy, MBG for OAB due to MS. Our objective is to determine the effect of BM-PFE with and without MBG in reducing the OAB Symptom Composite Score (OAB SCS). The OAB SCS is a validated measure that incorporates urinary frequency, urgency and incontinence episodes. The study design will also test differences in efficacy and tolerability between 25mg and 50mg doses of MBG.

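### The placebo arm cannot demonstrate the effect of BM-PFE, and self-chosen titration cannot test 25mg against 50mg; both contrasts should be labelled descriptive

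*Combined protocol and SAP*

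**What the plan says.** Four places describe what the trial will show about BM-PFE or about dose.

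- Protocol Summary, Rationale, on BM-PFE: "This design will demonstrate the effects of behavioral modification, including pelvic floor exercise on OAB through the placebo arm of the study".
- Protocol Summary, Rationale, on dose: "This titration will occur at about 5 weeks to allow a balanced period of time for recording response to the two dosages".
- Objective: "To assess the effect of pelvic floor exercise education with or without mirabegron (MBG) on overactive bladder symptoms".
- Background: "Our objective is to determine the effect of BM-PFE with and without MBG in reducing the OAB Symptom Composite Score", and then "The study design will also test differences in efficacy and tolerability between 25mg and 50mg doses of MBG".

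The design is set out elsewhere.

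- Treatment Regimen: "Group A and B will receive the same baseline education in pelvic floor exercise".
- The Randomization section allocates subjects to placebo or active drug and to nothing else.
- Under Investigational drug and Titration Visit, active subjects take 25mg up to the Titration Visit. They then choose, with the investigator, whether to stay or move to 50mg. Placebo subjects make the same choice with matching placebo.

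The Study Hypothesis concerns only the randomised contrast: "Treatment with Mirabegron will improve urinary urgency control beyond that achieved with pelvic floor exercises alone".

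The Statistical Analysis section lists summary statistics by treatment, a summary of percentage change from baseline, and significance testing. It compares groups by ANCOVA or another method. It describes no within-arm test and no dose comparison, and it does not label either as descriptive.

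**The concern.** The verbs *demonstrate*, *determine* and *test* promise causal conclusions from two contrasts that randomisation does not protect.

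For BM-PFE, every subject receives it, so the placebo arm offers only a before-after change. For dose, the groups form themselves after about five weeks of experienced benefit and side effects, and the higher dose only ever comes second.

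What is at stake is the reading of the results. The BM-PFE effect is written into the objective, and the planned summaries of change from baseline are the figures a reader would take as that effect. Results split by chosen dose could likewise be read as a dose effect.

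**Working it through.** **What can be reproduced.** The plan gives no effect size, SD or power for these contrasts. Its only figure is the sample size ("This will include 20 subjects taking mirabegron and 20 subjects taking placebo"), and 20 + 20 = 40 agrees. Every other input below is assumed, so the results are ranges and not predictions.

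**1. BM-PFE and regression to the mean.** The 72-hour screening diary decides entry. It requires at least 8 entries with urgency score 2 or more, and either at least 8 micturitions a day or at least 2 incontinence episodes. It is also the only pre-treatment diary, so it is the baseline.

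The entry rule was applied to simulated diaries with no intervention effect, using 1,000,000 subjects in each of 32 scenarios. The assumptions were:
- true voids per day: gamma, mean 8 or 10, SD 3;
- 72-hour counts: Poisson, with extra diary-to-diary CV of 15% or 25%;
- 2, 5, 10 or 20% of voids incontinent (score 5);
- 50% or 80% of the remainder urgent (score 3), and the others score 1.

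The mean score among eligible subjects changed on the second diary as follows:
- smallest: −1.2% (mean 10, CV 15%, 20% incontinent, 80% urgent; 96% eligible);
- largest: −12.8% (mean 8, CV 25%, 2% incontinent, 50% urgent; 46% eligible).

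A simpler check uses a truncated normal, with fall = (1 − r) × φ(c) / share passing:
- 90% passing and r = 0.85 gives 0.03 SD;
- 50% passing and r = 0.50 gives 0.5 × 0.399 / 0.5 = 0.40 SD.

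Placebo response and time would come on top of this.

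**2. Dose, with zero true dose effect.** Take baseline, week-5 and final scores with SD 1 and equal correlation ρ. Half of subjects up-titrate. Choice depends on the week-5 score plus noise of k times its SD. The covariance of week-5 score with the 0/1 choice is c = 0.399/√(1 + k²), and the variance of the choice is 0.25. The baseline-adjusted (ANCOVA) difference at the Final Visit, up-titrators minus others, is

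b = c·ρ(1 − ρ) / (0.25 − c²ρ²).

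- ρ = 0.6, k = 0: 0.399 × 0.24 / (0.25 − 0.159 × 0.36) = 0.0958 / 0.1927 = 0.50 SD.
- ρ = 0.8, k = 2: 0.178 × 0.16 / (0.25 − 0.0318 × 0.64) = 0.0285 / 0.2296 = 0.12 SD.

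Simulation over ρ = 0.4, 0.6, 0.8 and k = 0, 1, 2 gives the same range, 0.12 to 0.50 SD. Choice driven by week-5 change instead of level gives 0.16 to 0.49 SD. A logistic choice model (slope 0.5 to 2 per SD, correlation 0.5 or 0.7) gives 0.10 to 0.34 SD. If choice is unrelated to response, the difference is 0.

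The apparent direction depends on the analysis. In the logistic model, up-titrators look worse at the Final Visit after baseline adjustment, yet 0.14 to 0.60 SD better on change from week 5 to the end. In the equal-correlation model with level-driven choice, the raw change from baseline shows no difference at all.

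**3. Precision without confounding.** Within the 20 mirabegron subjects, with 18 df, the 95% CI half-width is 2.101 × √(1/k + 1/(20 − k)), where k is now the number up-titrating:
- 10/10: 2.101 × 0.447 = 0.94 SD;
- 7/13: 2.101 × 0.469 = 0.98 SD;
- 5/15: 2.101 × 0.516 = 1.08 SD.

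This assumes that all 20 contribute a final diary.

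**The case against.** The strongest reply is that these are sentences of motivation. The hypothesis is the randomised contrast. The Statistical Analysis section compares groups, ties superiority to the primary endpoint, and lists summaries apart from significance testing. Sample Size Considerations calls the study a preliminary pilot. No planned test or decision rule depends on the disputed wording. This stands in part and is why the point is not a major one. But the Objective section is not mere motivation, and it includes the BM-PFE effect. Nor does the Statistical Analysis section confine significance testing to the randomised contrast. The protocol does use a lesser label elsewhere, calling the bowel questionnaire exploratory, but not here.

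A second reply is that matching-placebo up-titration supplies a control. Placebo subjects who choose to up-titrate would show much of the same time and regression artefact. In the model above, with a constant 0.5 SD drug effect added, the artefact was nearly the same in both arms, and subtracting one from the other left at most about 0.05 SD. This also stands in part. However, it relies on a constant drug effect. If response to drug varies, choosers in the two arms are no longer alike. The feature keeps the blind but does not randomise dose, and no such comparison is planned.

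A reader might also infer that the plan commits to an invalid test. It does not: no within-arm or dose test is specified. The percentage-change summary is probably by arm, but only the preceding item on summary statistics says so.

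**Conclusion.** The wording is wrong as written; the fault is moderate to minor. The design cannot demonstrate a BM-PFE effect from the placebo arm, and it cannot test 25mg against 50mg, because neither contrast is randomised.

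That conclusion needs no assumption. The sizes do:
- about 1% to 13% from regression to the mean alone;
- about 0.1 to 0.5 SD of the score for a spurious baseline-adjusted dose difference if choice depends on week-5 response, and 0 if it does not.

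Only the half-width of 0.94 to 1.08 SD uses the plan's own N, and it still assumes a split and complete data.

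A reader might infer that the primary result is compromised. The documents do not support that: mirabegron versus placebo is randomised, BM-PFE is common to both arms, and regression to the mean is expected equally in both. Nor do they support a claim that bias of any given size will occur, since they give no SD, no correlation and no rule for how subjects choose.

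**What to change.** Reword four sections.

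- **Protocol Summary, Rationale.** Replace the sentence on demonstrating BM-PFE effects with: *The placebo-arm change from baseline is descriptive and not attributable to BM-PFE alone.* In the titration sentence, say that response at the two dosages is recorded descriptively.
- **Background.** Replace the claim to test dose differences with a statement that the study will describe efficacy and tolerability by chosen dose.
- **Objective, and the matching sentence in Background.** State the objective as the effect of adding mirabegron to BM-PFE.
- **Statistical Analysis.** Add: *The randomised contrasts are mirabegron versus placebo, on top of BM-PFE, at the Titration Visit (25mg) and at the Final Visit (flexible dose, as already specified). Within-arm change and results by chosen dose are descriptive, given with confidence intervals and without significance tests or causal claims.*

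The cost is a few sentences. No dose, titration rule, sample size, visit or data item changes, and by-dose reporting is kept. The sponsor gives up only the words *demonstrate* and *test* for two contrasts that cannot carry them.

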## Objective

To assess the effect of pelvic floor exercise education with or without mirabegron (MBG) on overactive bladder symptoms in people with multiple sclerosis (MS) based on the OAB Symptom Composite Score.

## Background

There are 400,000 Americans with MS and past and current surveys indicate that more than 80% report some bladder dysfunction, including 61% with urinary urgency. In MS, immune dysregulation and neurodegeneration in the central nervous system impairs normal micturition. Symptoms include frequency and/or urgency of urination, hesitancy in starting urination, nocturia and incontinence. Urological studies have shown the most common complaint is urinary urgency due to overactive bladder (OAB), with urinary retention less common. This is supported by urodynamic findings of detrusor hyperreflexia in 68% of a MS cohort. One study suggests that detrusor hyperreflexia is more severe when related to MS than when idiopathic. Urinary urgency and urge-incontinence symptoms have markedly negative impacts on physical functioning and mental-functioning health-related quality of life metrics in MS.

Potential treatments for OAB include behavioral modification, pelvic floor rehabilitation, oral or intravesical anticholinergic medications, desmopressin, duloxetine, intravesical injection of botulinum toxins, medicinal cannabis, or placement of external or indwelling catheters. Mirabegron (MBG) is the first beta-3 adrenergic agonist drug indicated for OAB treatment with symptoms of urge urinary incontinence, urgency and urinary frequency (see prescribing information). This was based on studies conducted in general populations having OAB symptoms and not stress incontinence. MBG has not been studied in MS.

Pelvic floor rehabilitation has a well-established role in the management of stress incontinence and idiopathic OAB. There is some evidence that pelvic floor exercise taught by physiotherapists over multiple sessions improves OAB in MS. However, access to pelvic floor physical therapy is limited by third-party payer coverage, availability of therapists with the necessary expertise and incurred expenses and time requirements for the patients. Behavioral modification, including pelvic floor exercise (BM-PFE) may be provided in a clinical setting using relevant educational materials. The BM-PFE component will offer an important educational benefit to all subjects interested in this study. Our center has a strong pelvic rehabilitation program with three therapists who are well-suited to produce the educational component of this study.

Adding MGB may yield greater results than BM-PFE alone. The standard starting dose is 25mg daily. An optional up-titration to 50mg is proposed, since some patients may respond better to the higher dosage, based on a Phase III trial including 25mg and 50mg daily treatment arms. This titration will occur at visit 3; 32-40 days post Baseline Visit, to allow a balanced period of time for recording response to the two dosages. Both dosages have been reported to be effective in treating OAB within 12 weeks.

This study explores the benefits of combining a brief BM-PFE educational program with a pharmacotherapy, MBG for OAB due to MS. Our objective is to determine the effect of BM-PFE with and without MBG in reducing the OAB Symptom Composite Score (OAB SCS). The OAB SCS is a validated measure that incorporates urinary frequency, urgency and incontinence episodes. The study design will also test differences in efficacy and tolerability between 25mg and 50mg doses of MBG.

## **Methodology**

We propose a parallel-group, randomized, double-blind placebo-controlled trial of MBG as add-on therapy to an educational pelvic floor exercise (BM-PFE) intervention to a cohort of 40 MS subjects with overactive bladder (OAB).

Active drug will be MBG 25mg daily with optional up-titration to 50mg daily at Titration (visit 3). Subjects will be enrolled at Baseline (visit 2) based upon scores for urinary urgency and micturition frequency in subject diary recorded during screening period.

Voiding diaries of a 72 hour period each will be utilized during the screening period, between Phone Visit 1 and Titration and between Phone Visit 2 and Final Visit. Subjects will record the time of each micturition and/or urgency episode, urine volume with each void, any episode of incontinence, and the severity of urgency using the OAB-SCS. This score accounts for frequency and the urgency components of OAB, including incontinence episodes.

